8.3 Serious Adverse Events

An SAE is defined as any untoward medical occurrence that at any dose:

- Results in death
- Is life-threatening (i.e. the subject was, in the opinion of the CI, at immediate risk of death from the event as it occurred); it does not refer to an event which hypothetically might have caused death if it were more severe
- Requires or prolongs inpatient hospitalization
- Results in persistent or significant disability/incapacity (i.e. the event causes substantial disruption of a person's ability to conduct normal life functions)
- Results in a congenital anomaly/birth defect
- Requires intervention to prevent permanent impairment or damage
- Is an important and significant medical event that may not be immediately life-threatening or resulting in death or hospitalization, but based upon appropriate medical judgment, may jeopardize the subject or may require intervention to prevent one of the other outcomes listed above.

AEs which do not fall into these categories are defined as non-serious. It should be noted that a severe adverse event need not be serious in nature and that a SAE need not, by definition, be severe.

In addition, a pre-existing event or condition that results in hospitalization should be recorded on the medical history. The hospitalization would not result in the event or condition being reported as a study-related SAE, unless, in the view of the PI, hospitalization was prolonged as a result of participation in the clinical trial or was necessary due to a worsening of the pre-existing condition. This is because the onset of the event (the reason for the procedure) occurred before the subject was entered in the trial. Hospitalization for cosmetics, non-emergency prophylaxis, or abortion does not

result in an SAE report, unless, in the view of the PI, hospitalization for these procedures was prolonged as a result of participation in the clinical trial.

8.4 Medical Emergencies

The sessions will be conducted in an outpatient research building on the campus of the Harbor-UCLA Medical Center, which is a 10 minute walk from the Emergency Department. The PI will conduct all experimental sessions accompanied by co-investigator [name]. The co-therapist or PI will be available via mobile phone or pager throughout the study if any problem occurs when a subject is not at the site. Subjects will continue to see their outside therapist throughout the study. For a recently completed Phase 2 trial, the sponsor has established contingency plans for responding to those AEs that appear most likely, based on a comprehensive review of literature described in the current IB. The same contingency plans and equipment will be used in this protocol.

8.5 Adverse Event Collection

The PI will be responsible for reviewing and confirming all AEs and SAEs collected during the study. The co-therapist or PI will collect AEs during study visits after enrollment.

All SAEs will be collected for the duration of the protocol. All SAEs which occur during the course of the trial, whether considered to be associated with the study drug or not, have to be reported within 24 hours of the CI's awareness of their occurrence. All SAE reports should be faxed to the sponsor. A fax number will be provided to the site in separate site-specific instruction for SAE reporting. In addition to the fax, the PI, or designee should call the Clinical Research Associate (CRA) during normal working hours and verbally inform the CRA of the SAE. During off business hours or if medical advice is needed immediately, the sponsor Medical Monitor will be called. SAE reporting instructions with all contact numbers will be provided to the site prior to study start.

The following symptoms will be assessed at baseline and exacerbations during the study will be tracked and categorized as mild, moderate, or severe on a separate Symptoms CRF log page: Persistent feelings of alienation, Rigidity, Tremor, Dystonic Symptoms, Akathisia, Increased Motor Activity, Decreased Motor Activity, Sensory Hyperarousal, Excitement/Agitation.

AEs to be collected during the study are:

- Serious Adverse Events (SAEs) will be collected from enrollment through termination.
- All AEs and spontaneously reported reactions will be collected on the day of and seven days after each experimental session or until they resolve.

- AEs requiring medical attention, including a doctor visit or treatment with prescription medication, will be collected from the first experimental session through the final integrative session after the second experimental session.
- AEs related to planned treatments or physician visits for baseline conditions collected in the Medical History will not be collected unless there is an exacerbation of the condition.
- Any AE leading to withdrawal will be collected throughout the study.
- All AEs related to changes in psychiatric status will be collected throughout the study.
- Any exacerbations of Symptoms recorded at Medical History will be collected throughout the study.

A Memory Aid Card will be provided to the subject on the last visit prior to the 6-month follow-up to record information on medications taken to treat SAEs, AEs leading to withdrawal and psychiatric AEs during the follow-up period during the follow-up period. The Memory Aid Card will not be collected, but information from the card will be used to aid the subjects in providing information to the CI.

9.0 Concomitant Medications and Tapering Instructions

The PI will record concomitant medications during screening. If the subject is being treated with psychiatric drugs at the time he or she is recruited into the study, the prospective subject will be encouraged to discuss medication tapering with his or her outside treating physician, if any, and will be required to give the PI permission to do so as well. The drugs will then be tapered in an appropriate fashion to avoid withdrawal effects. They will be discontinued long enough before the first experimental session to avoid the possibility of any drug interactions (the interval will be at least five times the particular drug's half-life).

Table 5: Medication Washout Table for MDMA studies

Generic Name	Brand Name	Half-life (hours) including active metabolites	Days for Washout
alprazolam	Xanax	11	3
aripiprazole	Abilify	75	16
atomoxetine	Strattera	5-24	5
bupropion	Wellbutrin	21	5
citalopram	Celexa	35	8
clonazepam	Klonopin	30-40	8
diazepam	Valium	20-70	15

duloxetine	Cymbalta	12	3
escitalopram	Lexapro	32	7
fluoxetine	Prozac	7-9 (days)	45
imipramine	Tofranil	6-18	4
lamotrigine	Lamictal	25	6
lorazepam	Ativan	12	3
mirtazapine	Remeron	20-40	8
olanzapine	Zyprexa	21-54	11
paroxetine	Paxil	21	5
prazosin	Minipress	2-3	1
quetiapine	Seroquel	6	2
risperidone	Risperdal	3-20	4
sertraline	Zoloft	26	6
temazepam	Restoril	8-12	3
trazodone	Desyrel	9	2
venlafaxine	Effexor	12	3
ziprazidone	Geodon	7	2
zolpidem	Ambien	2.5	<1

The therapists will request information about any changes in medication just prior to each experimental session. The PI will be responsible for reviewing and confirming all medications collected during the study.

All medications, over the counter (OTC) and prescription, will be collected from screening through seven days after the last experimental session. From the end of the seven days after the last experimental session through the 6-month follow-up visit, only prescription or OTC medications taken to treat AEs will be collected. Throughout the protocol all medications used to treat AEs will be collected as specified in Section 8.5 and all changes to psychiatric medications will be collected, including discontinuations or additions. Medications will be recorded on the concomitant medications CRF.

Subjects must be willing to refrain from taking any psychiatric medications during treatments received in Stage 1 and Stage 2. If the subject is on stimulants for ADHD at baseline, they can continue to use them at the same dose and frequency, as long as they utilize a washout period of at least five half-lives of the drug and active metabolites plus one week for stabilization before each experimental session and do not restart for ten days after each experimental session.

The PI may prescribe a designated rescue medication in the event of symptoms that require it during or after the experimental session (e.g. insomnia or severe anxiety that does not respond to other management). Rescue medications may be benzodiazepines such as lorazepam, or sedative hypnotics such as zolpidem, or atypical antipsychotics. Any atypical antipsychotic medications used during the experimental session or the week after should not be primarily metabolized by CYP2D6, such as quetiapine instead of risperidone. SSRIs, SNRIs, and MAOIs should not be used as rescue medications.

Subjects must agree that, for one week preceding the MDMA session:

- a. They will refrain from taking any herbal supplement (except with prior approval of the research team).
- b. They will refrain from taking any prescription or nonprescription medications (with the exception of non-steroidal anti-inflammatory drugs, acetaminophen, birth control pills, thyroid hormones, or other medications approved by the research team).

Subjects may return to taking psychiatric medications and discontinue birth control during the follow-up period if necessary. Subjects will receive a Memory Aid Card to record these medications between the final integrative visit in Stage 1 and the 6-month follow-up, as described in Section 8.5. Subjects will use this card to record changes in psychiatric medications that they will be asked about at the 6-month follow-up visit. Memory Aids will not be collected.

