4.0 Protocol Design

Twelve subjects meeting eligibility criteria will be enrolled. Throughout the study, the study therapists will maintain communication with the referring physician or therapist and any other health care providers requested by the subject. In consultation with their prescribing physician, any individuals taking psychiatric medications will taper off these medications, allowing for a washout period of at least 5 times the medication and active metabolite half-lives plus one week for stabilization before the experimental session. During the study, benzodiazepines or atypical antipsychotics may be used to alleviate severe distress or panic responses if other interventions are ineffective. Subjects who are in psychotherapy with an outside therapist at the time of enrollment may continue that therapy during the treatment period without increasing the number or type of sessions or changing type of psychotherapy until after the outcome assessment, one month after the second experimental session in Stage 1. After the treatment period, subjects may resume psychotropic medications and may change therapists or psychotherapy type.

Each of the 12 subjects will participate in two experimental MDMA-assisted therapy sessions of seven hours in duration within a brief course of non-drug therapy, including three preparatory sessions at the start of the study and three integrative sessions during the month after each experimental session. During preparatory sessions, subjects will learn what to expect during experimental sessions and complete pre-treatment assessments. The second preparatory session will include a comprehensive tour of the treatment location and introductions to all available research and support personnel who subjects are likely to see during experimental sessions. In-person visits will occur in a private room in an outpatient research facility. All in-person sessions after enrollment may be video recorded for the purposes of evaluating structural elements of therapy for effectiveness and feasibility. Video recordings will be used for research and training purposes during and after the study.

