A = At the beginning of the session; B = Approximately every sixty minutes; C = As needed; D = Approximately six hours post drug; E = Day 2 and Day 7 phone calls only; F = Reactions collected for seven days post experimental session; G = Independent Rater administered; H = May be recorded to video; I = Stage 2 subjects only; J = Only MDMA subjects will terminate.

Table 3. Time & Events Stage 2

Study Phase	Experimental Session	Integrative Sessions			Experimental Session	Integrative Sessions		
	V15	V16	V17	V18	V19	V20	V21	V22
Visit #	V15	V16	V17	V18	V19	V20	V21	V22
Visit Timing		1 day later	2 Wks later	2 Wks later	Appr. 1 Month after V15	1 day later	2 Wks later	2 Wks later
LSAS		✓ ^G	✓ ^G	✓ ^G		✓ ^G	✓ ^G	✓ ^G
C-SSRS	✓ ^{A, C, D}	✓ ^E	✓	✓	✓ ^{A, C, D}	✓ ^E	✓	✓
Feedback Questionnaire, Qualitative Interview								✓
Collect Concomitant Medication	✓	✓	✓	✓	✓	✓	✓	✓
End Medication Taper (if applicable)	✓ ^I							
Collect Serology Samples (OT, AVP, CORT)	✓			✓	✓			✓
Record to Video	✓	✓	✓	✓	✓	✓	✓	✓
General Wellbeing	✓	✓	✓	✓	✓	✓	✓	✓
Drug Screen	✓				✓			
Pregnancy Screen (if applicable)	✓				✓			
BDI-II, STAI		✓	✓	✓		✓	✓	✓
PSS		✓				✓		✓
IRI, RSES		✓				✓		✓
TASIT	✓				✓			✓
ERQ, TAS-20								✓
Administer Drug + Therapy	✓				✓			
Monitoring of BP, Pulse, and Temperature, SUD	✓ ^{A, B, C}				✓ ^{A, B, C}			
Integrative Therapy Session		✓	✓	✓		✓	✓	✓
Start 7 Days Integrative Phone Contact		✓				✓		
Spont. Reported Reactions & All Adverse Events	✓	✓ ^F	✓		✓	✓ ^F	✓	
Symptoms at Baseline	✓	✓	✓	✓	✓	✓	✓	✓
Adverse Events Requiring Doctor's Visit	✓	✓	✓	✓	✓	✓	✓	✓
Adverse Events Causing Withdrawal	✓	✓	✓	✓	✓	✓	✓	✓
SAEs	✓	✓	✓	✓	✓	✓	✓	✓
Termination								✓
Approximate Hours for Study Visit	8.0	1.9	1.7	2.1	8.0	1.9	1.7	2.7

A = At the beginning of the session; B = Approximately every sixty minutes; C = As needed; D = Approximately six hours post MDMA; E = Day 2 and Day 7 phone calls only; F = Reactions collected for seven days post experimental session; G = Independent Rater administered; H = May be recorded to video; I = At least 5 half-lives and 1 week before the experimental session.

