5.2.2 Preparatory Sessions and Baseline Measures

Subjects who do not complete all screening activities will not be enrolled. Eligibility may be discussed by phone after screening is complete and at the time Visit 3 is scheduled but the final confirmation will occur at Visit 3. If all inclusion criteria and no exclusion criteria are met, eligibility will be confirmed with the subject.

- Complete a final review of inclusion/exclusion criteria.
- Assess general wellbeing.
- Confirm eligibility and willingness to participate in study.
- Enroll subject and issue subject number.
- Ensure medical history and medication history is complete. After enrollment new events will be collected as AEs and new medications, as described in Section 8.5 and Section 9.0.
- Assess status of symptoms at baseline specific to the study population.
- Discuss medication tapering, if applicable. Upon confirmation of eligibility, the PI will consult the prescribing physician to initiate medication tapering for

subjects who must refrain from taking a psychiatric medication for the study. Tapering will follow a time course appropriate for the medication given its half-life, with the first experimental session scheduled to occur after complete washout.

The subjects will undergo three preparatory sessions lasting approximately sixty minutes each with their therapist team, prior to their first experimental session. The first preparatory session will take place at Visit 1 after enrollment confirmation. Baseline measures will be spread out among preparatory sessions in order to reduce participant fatigue from completion of measures.

The therapists will work with the subject to prepare for MDMA-assisted therapy. The therapists and subject will seek to form a strong working relationship with each other as the therapists help the subject prepare for upcoming experimental sessions. Preparatory sessions will promote a safe set and setting for confronting emotions and are intended to develop therapeutic alliance.

During preparatory sessions:

- a. Therapists may record all sessions to audio and video. Subjects may access video recordings from these sessions upon request via a secure and password protected website.
- b. Collect AEs and medications, as described in Section 8.5 and Section 9.0.
- c. Assess status of symptoms at baseline specific to the study population.

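### Protocol section 9.0 and Table 5 omit the one-week stabilization period that section 4.0 adds to the five-half-life washout

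*Protocol*

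**What the plan says.** Protocol section 4.0 covers every subject taking psychiatric medication and requires tapering, "allowing for a washout period of at least 5 times the medication and active metabolite half-lives plus one week for stabilization before the experimental session". Footnote I to Table 3 (section 4.1) gives the same rule for the end of the taper in Stage 2: "At least 5 half-lives and 1 week before the experimental session".

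Section 9.0 covers the same drugs. Its general sentence asks that they be stopped long enough to avoid interactions and defines this as follows: "the interval will be at least five times the particular" drug's half-life. Table 5 then lists 25 drugs with a half-life that includes active metabolites and a number of washout days. Neither the sentence nor the table mentions a further week or points back to section 4.0.

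Two later rules in section 9.0 also bear on the point:

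- Subjects on stimulants for ADHD must allow "at least five half-lives of the drug and active metabolites plus one week for stabilization before each experimental session".
- For the week before the MDMA session, subjects agree to the following: "They will refrain from taking any prescription or nonprescription medications". Listed exceptions apply, including other medications that the research team approves.

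Section 5.2.2 says that tapering follows the drug's half-life, "with the first experimental session scheduled to occur after complete washout". It does not say when washout counts as complete.

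**The concern.** Table 5 is the drug-by-drug tool a site would use to set the earliest dosing date, and it appears to leave out a week that section 4.0 makes mandatory. Because section 9.0 does state the week for ADHD stimulants, a reader can take its absence for the Table 5 drugs as intended.

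Three things depend on this:

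- **Time off the drug.** A tapering subject would have less stabilization time before the first session than section 4.0 requires.
- **Deviation status.** The same dosing date would comply with section 9.0 and be a deviation under section 4.0. SAP section 8.4 lists all protocol deviations by category.
- **Safety timing.** Sections 5.1.3 and 5.2.2 place a C-SSRS assessment after washout, so the end of washout needs one definition.

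Both rules require at least five half-lives, so the concern is not about drug interactions, and no bias in the LSAS comparison is alleged.

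**Working it through.** **Inputs.** Half-lives and listed days come from Protocol Table 5. Where a range is given I use its upper end. Fluoxetine at 9 days is 9 × 24 = 216 hours. Zolpidem, listed as under 1 day, is counted as 1. The added 7 days come from section 4.0.

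**Formulas, in days.**

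- Five half-lives: f = 5 × half-life (hours) / 24
- Section 4.0 minimum: f + 7
- Gap: (f + 7) − listed days
- Gap after the medication-free week: (f + 7) − max(listed days, 7)
- Corrected entry: f rounded up, plus 7

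**Step 1: reproduce Table 5.** Rounding f up gives the listed figure on 20 of 25 rows, and zolpidem (0.52) fits its entry of under 1. The other four are rounded down: clonazepam and mirtazapine (8.33, listed 8), olanzapine (11.25, listed 11) and risperidone (4.17, listed 4). Those fall short of five half-lives by 8, 8, 6 and 4 hours. No entry exceeds f by more than 0.79 days (lamotrigine, 6 − 5.21). The column is therefore five half-lives alone.

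**Step 2: compare with section 4.0.** Drugs with the same half-life and entry share a row.

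| Drug | Half-life (h) | f | Listed | f + 7 | Gap | Gap after 7-day floor | Corrected entry |
|---|---|---|---|---|---|---|---|
| alprazolam | 11 | 2.29 | 3 | 9.29 | 6.29 | 2.29 | 10 |
| aripiprazole | 75 | 15.63 | 16 | 22.63 | 6.63 | 6.63 | 23 |
| atomoxetine | 24 | 5.00 | 5 | 12.00 | 7.00 | 5.00 | 12 |
| bupropion, paroxetine | 21 | 4.38 | 5 | 11.38 | 6.38 | 4.38 | 12 |
| citalopram | 35 | 7.29 | 8 | 14.29 | 6.29 | 6.29 | 15 |
| clonazepam, mirtazapine | 40 | 8.33 | 8 | 15.33 | 7.33 | 7.33 | 16 |
| diazepam | 70 | 14.58 | 15 | 21.58 | 6.58 | 6.58 | 22 |
| duloxetine, lorazepam, temazepam, venlafaxine | 12 | 2.50 | 3 | 9.50 | 6.50 | 2.50 | 10 |
| escitalopram | 32 | 6.67 | 7 | 13.67 | 6.67 | 6.67 | 14 |
| fluoxetine | 216 | 45.00 | 45 | 52.00 | 7.00 | 7.00 | 52 |
| imipramine | 18 | 3.75 | 4 | 10.75 | 6.75 | 3.75 | 11 |
| lamotrigine | 25 | 5.21 | 6 | 12.21 | 6.21 | 5.21 | 13 |
| olanzapine | 54 | 11.25 | 11 | 18.25 | 7.25 | 7.25 | 19 |
| prazosin | 3 | 0.63 | 1 | 7.63 | 6.63 | 0.63 | 8 |
| quetiapine | 6 | 1.25 | 2 | 8.25 | 6.25 | 1.25 | 9 |
| risperidone | 20 | 4.17 | 4 | 11.17 | 7.17 | 4.17 | 12 |
| sertraline | 26 | 5.42 | 6 | 12.42 | 6.42 | 5.42 | 13 |
| trazodone | 9 | 1.88 | 2 | 8.88 | 6.88 | 1.88 | 9 |
| ziprasidone | 7 | 1.46 | 2 | 8.46 | 6.46 | 1.46 | 9 |
| zolpidem | 2.5 | 0.52 | 1 | 7.52 | 6.52 | 0.52 | 8 |

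No row reaches f + 7. Gaps run from 6.21 days (lamotrigine) to 7.33 days (clonazepam, mirtazapine).

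**Step 3: allow for the medication-free week.** That week runs concurrently with washout, so it sets a floor of 7 days and does not add 7 days. The eight drugs listed at 7 days or more gain nothing from it: aripiprazole, citalopram, clonazepam, diazepam, escitalopram, fluoxetine, mirtazapine and olanzapine stay 6.29 to 7.33 days short. For the other 17 the remaining gap is (f + 7) − 7 = f, from 0.52 (zolpidem) to 5.42 (sertraline) days.

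**The case against.** The strongest reply is that the two rules do not truly conflict. Section 9.0 sets a minimum for avoiding interactions, section 4.0 sets a stricter one with stabilization as its separate aim, and an interval meeting section 4.0 meets both. Table 5 could then be a generic pharmacokinetic reference, as its title suggests, with the extra week to be added. The principal investigator at the single treating site confirms tapering and could apply section 4.0. The stimulant rule may restate the week only because those drugs can be continued between sessions.

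This shows that a careful reader of the whole protocol can comply. It does not make section 9.0 and Table 5 correct as written. Section 4.0 counts the week within the washout period, the table's days are headed as washout, and nothing tells the user to add seven. Whether the stimulant wording was deliberate cannot be known; the point is only that it invites the wrong reading.

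Two further objections affect emphasis. First, the team's power to approve exceptions to the medication-free week is unlikely to extend to psychiatric drugs, which inclusion criterion 8 and section 9.0 bar separately. The table above treats the 7 days as firm; any approved exception would widen the gaps for the 17 shorter-washout drugs. Second, the rounding of four entries is a matter of hours, arises only at the upper half-life, and is a minor tidy-up.

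**Conclusion.** The concern holds. Section 9.0 and all 25 entries in Table 5 give five half-lives, while section 4.0 and the Table 3 footnote require a further week. Taken alone, the table permits dosing 6.2 to 7.3 days too early by section 4.0. With the medication-free week enforced, the shortfall stays at 6.3 to 7.3 days for eight drugs and is 0.5 to 5.4 days for the other 17.

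These figures assume the upper end of each half-life range and zolpidem counted as one day. The practical effect is limited to subjects who taper a listed drug, an unknown subset of the 12, at a site that works from section 9.0. It concerns stabilization time and deviation status. It does not touch the analysis or the treatment comparison.

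**What to change.** Bring section 9.0 into line with section 4.0.

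- **Sentence.** Replace the parenthesis in section 9.0 with wording such as: *at least five half-lives of the drug and its active metabolites, followed by a further seven days for stabilization*.
- **Table 5, preferred.** Replace the days with the corrected entries in the table above. They run from 8 (prazosin, zolpidem) to 52 (fluoxetine) and include clonazepam 16, mirtazapine 16, olanzapine 19 and risperidone 12.
- **Table 5, alternative.** Keep the column, label it as five half-lives before the stabilization week, and round clonazepam, mirtazapine, olanzapine and risperidone up to 9, 9, 12 and 5.

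The cost is one sentence and one table column. The visit schedule does not change, because section 5.2.2 already places the first session after complete washout. Some subjects would wait up to about a week longer than Table 5 now implies, which section 4.0 already requires.
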